Based on this hypothesis, we already investigated the prognostic significance of peripheral blood immune cell counts in HR+/HER2- aBC patients treated with ET+CDK4/6i. 42 In fact, although the main mechanism of CDK4/6i-mediated anticancer activity consists in cell autonomous anticancer effects, preclinical evidence indicates the CDK4/6i ability to stimulate antitumor immunity. To preliminary investigate if peripheral blood immune cell counts or composite immune parameters, as evaluated at baseline or during CDK4/6i therapy, are associated with efficacy of any-line ET+CDK4/6i, we performed an analysis in 638 HR+/HER2- aBC patients treated in six Italian centers. In this study (PALMARES study), we investigated if baseline or ontreatment peripheral blood immune cells, such as lymphocytes, neutrophils, platelets or monocytes, or the composite scores neutrophil-to-lymphocyte ratio (NLR), platelet-to-lymphocyte ratio (PLR), monocyte-tolymphocyte ratio (MLR) or the Pan-Immune Inflammatory Value (PIV), are associated with patient PFS. Peripheral blood immune cell values were collected at baseline (T0), 2 weeks after treatment initiation (T1) and before fourth cycle initiation, approximately 12 weeks after treatment initiation (T2). We used Random Forest models to select clinically relevant covariates (line of therapy for advanced disease, ECOG PS, presence of liver metastases, number of metastatic sites, patient age, disease-free interval (DFI), percentage of Ki-67-positive cells in primary tumor specimens and presence of ER expression in primary tumor specimens) to adjust the role of peripheral blood immune cells in multivariable cox models. Median patient age in this cohort of patients was 61 years (IQR: 52-70 years). The majority of patients were postmenopausal (n=530; 83.1%), had an ECOG PS of 0 (n=464, 72.8%) and were treated with palbociclib (n=529; 82.9%). Approximately half of enrolled patients received CDK4/6i in the first-line setting (n=335; 52.5%) and had visceral disease (n=334; 52.4%). Among all the considered peripheral blood immune variables (neutrophils, platelets, lymphocytes and monocytes, the NLR, the PLR, the MLR and also the PIV), only baseline lymphocyte values and their precocious modulation (i.e. after 2 weeks of treatment), were independently associated with patient PFS.42

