The three CDK4/6i molecules are characterized by minor differences in terms of chemical composition, but with significant consequences in clinical terms. In particular, ribociclib and abemaciclib, unlike palbociclib, have a higher affinity for CDK4 than CDK6. Palbociclib and ribociclib, on the other hand, have much bulkier substituents at the ATP-binding pocket than abemaciclib, resulting in the latter's lower selectivity for CDK4 and CDK6 and higher pleiotropic affinity towards other members of the cyclin-dependent kinase family. This justifies the higher off-target activity, as well as toxicity, of abemaciclib compared to the other two drugs. From a pharmacokinetic point of view, palbociclib and ribociclib have a higher affinity for glycoprotein P and the efflux transporter Breast Cancer Resistance Protein (BCRP), resulting in lower central nervous system (CNS) permeability than abemaciclib. Due to different pharmacokinetic properties, the three CDK4/6i are approved for administration in different fashion, with abemaciclib prescribed in a continuous schedule, that provides sustained inhibition of CDK4 and CDK6, while palbociclib and ribociclib given in intermittent dosing with a 3-weeks-on, 1-week-off schedule. OK6

As a consequence of different pharmacokinetic and pharmacodynamics properties, palbociclib, ribociclib and abemaciclib are characterized by a different toxicity profile. In particular, while palbociclib and ribociclib

are characterized by a more frequent bone marrow toxicity, ribociclib treatment is associated with a higher rate of liver toxicity and prolongation of the corrected QT (QTc) tract on electrocardiographic tracing, while abemaciclib is associated with an increased rate of gastrointestinal disorders, particularly in terms of diarrhea.^{52,53}

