- To test the association between blood lymphocyte counts at baseline, or their precocious ontreatment modifications (T1: 2 weeks after treatment initiation, and T2: before fourth cycle initiation, approximately 12 weeks after treatment initiation) and rwPFS, TTNT-D, TTC-D and OS of HR+/HER2- patients treated with first-line ET plus CDK4/6i;
- To evaluate the association between peripheral blood crude cell counts, namely whole blood cells, neutrophils, monocytes and platelets, as evaluated at baseline and as precocious on-treatment modifications, and patient rwPFS, TTNT-D, TTC-D and OS;
- To evaluate the association between baseline composite parameters, such as the Neutrophil-to-Lymphocyte ratio (NLR), the platelet-to-lymphocyte ratio (PLR), the monocyte-to-lymphocyte ratio (MLR), or the Pan-Immune Inflammation Value (PIV), and patient PFS;
- To evaluate the association between precocious on-treatment modifications (i.e., 2 weeks and ∼12 weeks after treatment initiation) of NLR, PLR, MLR and PIV, and patient PFS;
- To evaluate the association between HER2 status (HER2-low vs. HER2-0; HER2 2+ with negative ISH vs. HER2 1+ vs. HER2-0) in the primary tumor and rwPFS, TTNT-D, TTC-D and OS;
- To evaluate the association between HER2 status (HER2-low vs. HER2-0; HER2 2+ with negative ISH vs. HER2 1+ vs. HER2-0) in one metastatic site (subjected to biopsy before CDK 4/6 inhibitor initiation), and rwPFS, TTNT-D, TTC-D and OS;
- To explore pattern of progression of HR+/HER2- aBC after ET plus CDK4/6i treatment;
- To test the effect on rwPFS, TTNT-D, TTC-D and OS of mastectomy in patients with *de novo* HR+/HER2- aBC.

Study Population

Inclusion criteria:

- Pre- and Post-menopausal patient (woman OR man)
- Age≥18 years
- Diagnosis of aBC. HR+/HER2- aBC, as defined as at least 1% estrogen receptor (ER) and/or progesterone receptor (PgR) positivity at IHC. HER2 negativity is defined on the basis of an IHC score of 0, 1+, or 2+ with absence of gene amplification at in situ hybridization (ISH) analyses.
- Have received or are candidate to receive treatment with palbociclib, ribociclib or abemaciclib in combination with endocrine therapy as first-line treatment for HR+/HER2- aBC.

Exclusion criteria:

- Less than 3 months of follow up from the CDK4/6i start to the date of data cut-off;
- Have received CDK4/6i as monotherapy;
- Have received CDK4/6i as adjuvant treatment for localized disease.

Data collection

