For the "Translational sub-study" purposes, tumor samples related to patients enrolled in the RWD sub-study will be considered. If multiple tumor samples are available, the ones to be used for the study has to be chosen as specified in the section "Translational sub-study". Tumor materials have to be shipped to the Sponsor center at the moment of the conduction of translational analyses, attributing the same pseudonymized code used for the other sub-study. The remaining unused tumor tissue will be sent back to the pathology laboratory at the end of the study.

Statistical considerations

Statistical design

Based on pivotal trials showing a statistically significant OS advantage for ribociclib and abemaciclib, but not for palbociclib in the endocrine resistant setting, and clinically meaningful OS advantage for ribociclib and abemaciclib, but not for palbociclib in the endocrine sensitive setting, we will hypothesize a difference of 20% in terms of OS between ribociclib versus palbociclib and between abemaciclib and palbociclib. To detect this difference with 80% power with a two-sided alpha error of 0.05, a sample size of 3258 patients reaching 977 OS events will be required. The prognostic role of CDK4/6i drug will be weighed for clinically and biologically relevant characteristics.⁸⁹

Since the number of patients enrolled in the other sub-studies depends on the sample size of the RWD sub-study, no formal statistical calculation has been performed for 2 to 5 PALMARES-2 sub-studies.

Statistical methods

Version 1.1, 01Aug2024

Standard descriptive statistics will be used to describe clinical and biological patients' characteristics. The median and interquartile range (IQR) were reported for continuous variables. Categorical variables were summarized as percentages of available data. To evaluate differences, in terms of clinic-pathological characteristics, among different CDK4/6i groups, we will use the Kruskal-Wallis Rank Sum test for

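### The 12-week blood count follows an off week on palbociclib and ribociclib but falls on continuous abemaciclib, so the pooled on-treatment change partly records the drug

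*Protocol*

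**What the plan says.** The secondary objectives of sub-study (1), Real world data, ask whether baseline lymphocyte counts or their early changes are associated with rwPFS, TTNT-D, TTC-D and OS. The time points are "T1: 2 weeks after treatment initiation" and "T2: before fourth cycle initiation, approximately 12 weeks after treatment initiation". The next objectives treat the other cell counts in the same way. Changes in NLR, PLR, MLR and PIV at about 2 and 12 weeks are related to PFS. None of these objectives is split by drug. Many of the objectives listed before them in the same section do specify a comparison among the three inhibitors.

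The background section on differences between the three drugs describes "palbociclib and ribociclib given in intermittent dosing with a 3-weeks-on, 1-week-off schedule" and "abemaciclib prescribed in a continuous schedule, that provides sustained inhibition of CDK4 and CDK6". It adds that palbociclib and ribociclib "are characterized by a more frequent bone marrow toxicity".

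Under Statistical design, the protocol states that "we will hypothesize a difference of 20% in terms of OS between ribociclib versus palbociclib and between abemaciclib and palbociclib", with 977 OS events. Statistical methods plans multivariable Cox regression without naming covariates for the blood-count objectives.

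The Data collection list of the same sub-study gives complete blood counts at baseline, 15 days, 30 days and progression. The drug used is also collected.

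**The concern.** T2 is defined by cycle number, and the cycle has a different shape under the two kinds of schedule. The same label therefore means the end of an off week for two drugs and an on-drug value for the third. Marrow toxicity also differs by drug, so the change from baseline should depend on which drug was given. The plan assumes that drug also affects OS. If the drug is left out of the model, it confounds the pooled association, and a count change with no prognostic meaning within any drug could appear prognostic.

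The time points match those of the sponsor's earlier PALMARES study, described in the background. There, 529 of 638 patients (82.9%) received palbociclib, so the schedules were little mixed. The adjustment covariates listed for that study do not include the drug. PALMARES-2 is built to compare all three drugs, so the mixing matters more here.

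**Working it through.** **Timing.** One cycle of 3 weeks on and 1 week off is 21 + 7 = 28 days. Three cycles take 3 × 28 = 84 days = 12.0 weeks, which reproduces the protocol's approximate 12 weeks. The off week of cycle 3 is days 78 to 84. A draw just before cycle 4 therefore comes after 7 drug-free days on palbociclib or ribociclib and 0 on abemaciclib. T1, at about day 15, falls within the 21 on-drug days for all three.

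**Which drugs differ in what.** The schedule and the marrow-toxicity statement both separate abemaciclib from the other two. The OS hypothesis separates palbociclib from the other two. Ribociclib shares palbociclib's schedule and abemaciclib's assumed OS effect, so the two contrasts overlap only in part.

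**Size under the null within drug.** Inputs from the protocol:
- 977 deaths;
- the 20% OS difference, read here as HR 0.80 (the protocol does not name the scale), so |ln 0.80| = 0.2231.

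Assumed inputs, which the documents do not give:
- a shift *d* in the T2 change for abemaciclib only, in within-drug SDs;
- drug shares, with *p* for palbociclib and *a* for abemaciclib;
- no within-drug association;
- a usable T2 count for every death.

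Formulas, drug omitted from the model:
- covariance of change and log hazard: C = 0.2231 × d × a × p
- variance of the pooled change: V = 1 + d² × a(1 − a)
- pooled |log HR| per within-drug SD = C / V
- z = (C / √V) × √977, with √977 = 31.26
- rejection rate = Φ(z − 1.96) + Φ(−z − 1.96)

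Example with equal thirds and d = 1: C = 0.2231 × 1/9 = 0.0248 and V = 1 + 2/9 = 1.222. The log HR is 0.0203 (HR 0.980), z = 0.0248 / 1.1055 × 31.26 = 0.70, and the rejection rate is 10.8%.

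| Shares palbociclib/ribociclib/abemaciclib | d = 0.5 | d = 1.0 | d = 1.5 |
|---|---|---|---|
| Equal thirds | 6.6% (HR 0.988) | 10.8% (0.980) | 15.8% (0.975) |
| 40/40/20 | 5.9% (0.991) | 8.1% (0.985) | 11.1% (0.980) |
| 60/20/20 | 7.0% (0.987) | 12.2% (0.977) | 19.0% (0.971) |

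Hazard ratios are written for a shift in the direction that makes them fall below 1. The opposite shift gives their reciprocals and the same rejection rates. In a model stratified by drug, all comparisons are made within drug, so this source of bias disappears.

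**Collection times.** The objectives need a blood count before cycle 4. The sub-study's own list has none. The collection before the fourth cycle in sub-study (2), Toxicity – Comorbidity, lists hepato-renal parameters, not blood counts.

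**The case against.** The strongest reply is that covariates and strata for a secondary biomarker model belong in a statistical analysis plan, which is not shown. The protocol nowhere says the drug will be left out, and a model containing it would largely remove the confounding. That stands, and it limits the force of the point. It does not dispose of it, because the protocol itself fixes T2 by cycle number and words these objectives over all patients. Even a drug-adjusted model would use one label for an off-week value and an on-drug value.

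A second reply is that the objectives ask about association, and a marker carrying some drug information can still be prognostic. That is fair. But a reader of the result would want to know whether the count adds anything once the drug is known.

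A third is that off-week recovery and more frequent marrow suppression on palbociclib and ribociclib could offset each other. The documents cannot settle this.

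Three stronger readings are tempting and are not supported:
- **Much larger error rates.** Two equal drug groups, with count shift and OS effect falling on the same split, give z = 0.2231 × d × 0.25 / √(1 + 0.25d²) × 31.26 = 0.85, 1.56 and 2.09 for d = 0.5, 1.0 and 1.5. The rejection rates are then 14%, 34% and 55%. In this protocol the two splits differ, so these rates do not apply.
- **T1 as the clean time point.** All three drugs are being taken at T1, but the stated difference in marrow toxicity applies there as well. T1 also carries drug information.
- **Reversal of a true association, or distorted recovery from T1 to T2.** Only the null case is computed here, and change from T1 to T2 is not a stated objective.

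**Conclusion.** The point holds as a modest but real design weakness. The difference in what T2 measures follows directly from the protocol's own schedules. The consequence is some confounding by drug if the pooled models omit it: about 6% to 19% false positives instead of 5%, with a pooled hazard ratio of about 0.97 to 0.99 per SD. Those figures are illustrative. They rest on assumed shifts and drug shares, on reading the 20% as HR 0.80, and on all 977 deaths having a T2 count. Fewer usable deaths would lower the rates, since z scales with the square root of the number of events. The illustration covers OS only, because that is the only outcome for which the protocol states an assumed drug difference. The missing 12-week blood count in the collection list is a separate inconsistency and needs no assumption.

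**What to change.** State in the protocol, or confirm in the analysis plan, that:
- the on-treatment blood-count models at both T1 and T2 are stratified by the CDK4/6 inhibitor received;
- the drug-by-change interaction is reported alongside any pooled estimate;
- T2 is interpreted as an off-week value for palbociclib and ribociclib and an on-drug value for abemaciclib.

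Reconcile the T2 definition in the objectives with the Data collection list of the same sub-study, which has no blood count at about 12 weeks.

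The modelling change needs only wording, because the drug is already recorded. Its price is slightly less precision. No change to treatment or schedules is implied.

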- Electrocardiographic parameters, in particular specific conduction alterations or arrhythmias and QTc value according to Fridericia, collected at baseline, after 15 and after 30 days from start;
- Patient comorbidity, understood as concomitant disease at the start of treatment with CDK4/6i ascertained by the physician and classified in macro-areas (e.g. cardiological, respiratory, metabolic, infectious, chronic diseases such as diabetes mellitus type 2);
- Concomitant therapies, initiated and ongoing before the start of treatment with CDK4/6i, reported as drug classes (e.g. steroid therapy, antibiotic therapy, proton pump inhibitors);
- Blood glucose and body mass index at baseline of CDK4/6i treatment.

(3) Medical imaging sub-study

Objectives and endpoints of the sub-study

Primary objective:

- To build a model able to predict prognosis of HR+/HER2- aBC patients treated with first-line ET+CDK4/6i using radiomics features extracted from baseline radiological images;
- To build a model able to predict prognosis of HR+/HER2- aBC patients treated with first-line ET+CDK4/6i using radiomics features extracted from baseline radiological images;
- To combine radiomics and pathomics features with clinical data to build a model able to predict prognosis of HR+/HER2- aBC patients treated with first-line ET+CDK4/6i;

Secondary objectives:

- To combine radiomics features with clinical data, pathomics, genomics and transcriptomics features to build a model able to predict prognosis of HR+/HER2- aBC patients treated with first-line ET+CDK4/6i;
- To build a model able to classificate HR+/HER2- aBC patients treated with first-line ET+CDK4/6i in early and late progressors using radiomics features extracted from baseline radiological images;
- To build a model able to predict prognosis of HR+/HER2- aBC patients treated with first-line ET+CDK4/6i using baseline radiomics features and early radiomics modifications detected from first on-treatment radiological evaluation;
- To build a model able to predict molecular characteristics, such as *PIK3CA* and *ESR1* mutational status, of HR+/HER2- aBC patients treated with first-line ET+CDK4/6i using radiomics features extracted from baseline radiological images;
- To build a model able to predict molecular characteristics, such as *PIK3CA* and *ESR1* mutational status, of HR+/HER2- aBC patients treated with first-line ET+CDK4/6i using radiomics features extracted from digitalized HE slides;
- To build a model able to predict intrinsic BC subtypes, defined by PAM50 panel on transcriptomic analyses, of HR+/HER2- aBC patients treated with first-line ET+CDK4/6i using radiomics features extracted from baseline radiological images;
- To build a model able to predict intrinsic BC subtypes, defined by PAM50 panel on transcriptomic analyses, of HR+/HER2- aBC patients treated with first-line ET+CDK4/6i using radiomics features extracted from digitalized HE slides.

Study Population

The same inclusion and exclusion criteria adopted for the RWD sub-study will be adopted for the present sub-study, for the only exception of the following inclusion criterion:

- Availability of at least one of the following two data:
 - A baseline Computerized Tomography (CT) scan or 18F-Fluorodeoxyglucose Positron Emission Tomography (FdG-PET)
 - A digitalized pathology slides derived from biopsy of metastatic sites and/or from primary tumor biopsy and/or from surgery specimen.

Data collection

This sub-study encompasses the collection of medical images of patients enrolled in the PALMARES-2 RWD sub-study. Two type of images will be collected:

- Radiological images: CT scan, or FdG-PET scan, performed at the baseline of CDK4/6i, i.e. up to three months before the treatment start until one week after the start; the CT scan should include at

least the thorax and abdomen scanning; both pre- and post-contrast acquisition will be collected. CT scan, or FdG-PET, performed as the first radiological evaluation will be collected as well to assess early radiomics modifications and their effect on survival outcomes. For the purposes of the "Subsequent lines" sub-study (as detailed below, in the (5) section), CT scan, or FdG-PET scan, performed at the baseline of each of the subsequent line of therapy will be collected as well.

Digitalized pathology slide: hematoxylin and eosin (HE) slides coming from diagnostic biopsy or surgical specimens will be digitalized and collected in a pre-defined folder. Both slides from primary tumor and from metastatic sites that underwent biopsy assessment will be collected, if available. If more than one metastatic biopsy has been performed during the course of patient's disease, all the HE slides should be collected, if available. If a patient did not undergo neoadjuvant treatment, diagnostic biopsy of the breast or surgical tumor slide could be collected equivalently; otherwise, the diagnostic biopsy performed before treatment initiation should be taken.

(4) Translational sub-study

Objectives and endpoints of the sub-study

Primary objective:

- To find the mutational status of a gene, or a subset of genes, associated with differential survival outcomes (rwPFS, TTNT-D, TTC-D and OS) of HR+/HER2- aBC patients treated with first-line ET+CDK4/6i;
- To find transcriptomic differential gene expression, or differential expressed pathways, associated with differential survival outcomes (rwPFS, TTNT-D, TTC-D and OS) of HR+/HER2- aBC treated with first-line ET+CDK4/6i.

Secondary objectives:

- To test the effect of PAM50 intrinsic subtype on survival outcomes (rwPFS, TTNT-D, TTC-D and OS) of HR+/HER2- aBC patients treated with first-line ET+CDK4/6i;
- To combine genomics and transcriptomics features with clinical data and radiomics and pathomics features, to build a model able to predict prognosis of HR+/HER2- aBC patients treated with first-line ET+CDK4/6i;
- To test the association between agnostic features included in radiomics model and transcriptomic pathways and mutational status.

Study Population

The same inclusion and exclusion criteria adopted for the RWD sub-study will be adopted for the present sub-study, for the only exception of the following inclusion criterion:

Availability of adequate tumor sample (see Data Collection below) from biopsy of metastatic sites and/or from primary tumor biopsy and/or from surgery specimen.

Data collection

This sub-study encompasses the collection of tumor samples of patients enrolled in the PALMARES-2 RWD sub-study. At least one formalin-fixed paraffin-embedded tumor block will be collected from diagnostic biopsy or surgical specimens, performed for diagnostic purposes as per clinical practice. Both tumor samples from primary tumor and from metastatic sites underwent biopsy will be collected, if available. If more than one metastatic biopsy has been performed during the course of patient's disease, all the non-stained slides and/or tumor blocks should be collected, if available. If a patient did not undergo neoadjuvant treatment, diagnostic biopsy of the breast or surgical tumor slide could be collected equivalently; otherwise, the diagnostic biopsy performed before treatment initiation should be taken.

(5) Second and further lines sub-study

Objectives and endpoints of the sub-study

Primary objective:

To build a model based on clinical, radiomics and pathomics data to select the best treatment option in terms of OS in HR+/HER2- aBC patients progressing after first-line ET+CDK4/6i.

Secondary objectives:

- To build a model based on clinical data to select the best treatment option in terms of OS in HR+/HER2- aBC patients progressing after first-line ET+CDK4/6i.
- To build a model based on clinical, radiomics, pathomics, genomics and transcriptomics data to select the best treatment option in terms of OS in HR+/HER2- aBC patients progressing after firstline ET+CDK4/6i.
- To assess the efficacy in terms of rwPFS and OS of second and subsequent line of therapy in a realworld setting of HR+/HER2- aBC patients progressing after first-line ET+CDK4/6i.

Study Population

The same inclusion and exclusion criteria adopted for the RWD sub-study will be applied for the present sub-study, for the only exception of the following inclusion criteria: Version 1.1, 01Aug2024

- Clinical, biochemical or radiological progression on CDK4/6i+ET first-line treatment
- Second-line therapy start after CDK4/6i+ET progression
- Data availability about at least one of the subsequent lines, including at least the treatment line of therapy, treatment start date, treatment progression date or last follow up, type of treatment and drug used.

Data collection

The study involves the collection of RWD of patients enrolled in the PALMARES-2 RWD study, who started a second line therapy after CDK4/6i progression. Data will be collected at the study centers in the same manner of RWD sub-study. Data collected within this sub-study will include the type of treatment performed (i.e. ET-based therapy, chemotherapy, other) and line of therapy for metastatic disease for which the treatment has been performed; treatment start date and progression date. Data derived from medical images and biological samples collected in the context of sub-study (3) and (4) will be used to pursue the objectives of this sub-study.

Study procedures

Informed consent process and patients' enrollment

Patients who are alive at the time of study conduction will be asked to sign the informed consent for the study partecipation and for treatment of personal data for research purposes, during the first clinical visit. Patients with available material to conduct analyses for the translational sub-study will be asked to the use of data generated from available material for the scientific purposes planned for the present study. It will also be asked to consent to receive unexpected genetic-hereditary information, should it emerge from the analysis of tumor samples.

For patients who are not alive at the moment of study initiation and data collection, the study will adhere to the UE-Reg 2016/679 - GDPR rules for the protection of personal data. In accordance with the Declaration of Helsinki and other applicable regulations, a subject, or his/her legal representative, has the right to withdraw from the study at any time and for any reason without prejudice to his/her future medical care. 88

Data protection procedures

Patients are assigned by the local investigator a unique progressive identifier code, that will be used for all the tasks implied in the study. The pseudonymization procedure will ensure the unique identification of patients still keeping adequate data security. This pseudonymized code will used to save medical images

once shared with the Sponsor center. The same code used to mark biological samples at the moment of the shipment to the centralization for analyses conduction.

Clinical data collection and management

Clinical real world data will be collected by centers in ad hoc document in .xlsx format. At pre-specified data cut-off (see sections below), data collected will be shared with the Sponsor for data analyses. Investigators at study centers could be required to modify data in case of data inconsistencies encountered during data analyses.

All consecutive HR+ HER2- aBC patients treated with first-line ET plus CDK 4/6i as per clinical practice in the time interval between January 2017 and December 2030 will be enrolled retrospectively and prospectively. Data will be collected in a continuous manner and will be shared with the Sponsor center on an annual basis, at pre-specified data cut-offs. Data cut-offs will occur annually, at certain cutoffs falling on 1st January of each year. Taking into account the time interval and the centers involved, approximately 2000 patients will be included at the first data cut-off of 1st January 2024. Those patients who have already concluded the treatment at the time of study inclusion will be evaluated for clinical outcomes (i.e. PFS, OS) and biological parameters of interest will be retrospectively collected. Patients who are still receiving ET plus CDK4/6i at the time of inclusion in the study will be evaluated for the same variables until the end of the study. At the time of data collection and analysis, these patients will be censored for the events of interest (e.g. progression, death) if these events have not occurred yet.

[figure not shown]

Figure 2. PALMARES-2 study expected timeline and enrollment. EC: ethical committee; pts: patients.

Medical images collection and sharing

The medical images, collected within the timeframe specified in the appropriate section (see section "Medical images sub-study"), will be collected locally in the individual centers, pseudonymised and uploaded to an ad hoc secure sharepoint. A folder will be set up for each individual center participating in this sub-study, so that only the center uploading the images and the Sponsor center itself will be able to access them.

Tumor samples collection, storage and shipment

For the "Translational sub-study" purposes, tumor samples related to patients enrolled in the RWD sub-study will be considered. If multiple tumor samples are available, the ones to be used for the study has to be chosen as specified in the section "Translational sub-study". Tumor materials have to be shipped to the Sponsor center at the moment of the conduction of translational analyses, attributing the same pseudonymized code used for the other sub-study. The remaining unused tumor tissue will be sent back to the pathology laboratory at the end of the study.

Statistical considerations

Statistical design

Based on pivotal trials showing a statistically significant OS advantage for ribociclib and abemaciclib, but not for palbociclib in the endocrine resistant setting, and clinically meaningful OS advantage for ribociclib and abemaciclib, but not for palbociclib in the endocrine sensitive setting, we will hypothesize a difference of 20% in terms of OS between ribociclib versus palbociclib and between abemaciclib and palbociclib. To detect this difference with 80% power with a two-sided alpha error of 0.05, a sample size of 3258 patients reaching 977 OS events will be required. The prognostic role of CDK4/6i drug will be weighed for clinically and biologically relevant characteristics.⁸⁹

Since the number of patients enrolled in the other sub-studies depends on the sample size of the RWD sub-study, no formal statistical calculation has been performed for 2 to 5 PALMARES-2 sub-studies.

Statistical methods

Version 1.1, 01Aug2024

Standard descriptive statistics will be used to describe clinical and biological patients' characteristics. The median and interquartile range (IQR) were reported for continuous variables. Categorical variables were summarized as percentages of available data. To evaluate differences, in terms of clinic-pathological characteristics, among different CDK4/6i groups, we will use the Kruskal-Wallis Rank Sum test for

continuous variables and the Chi-square and Fisher exact tests for categorical variables. Unpaired t-test will be used to compare numeric variables, at baseline and different timepoints. Classic survival analysis methods will be used to evaluate patient survival outcomes and survival curves will be obtained through the Kaplan–Meier method. Follow-up times will be estimated using the reverse Kaplan–Meier method. Multivariable analysis will be performed through Cox regression modeling to estimate the effects of covariates. To homogenize patients' characteristics among treatment groups, additional adjustment techniques will be eventually used, such as propensity score matching (PSM) and inverse probability of treatment weighting (IPTW). Estimated weights will be then incorporated into a weighted Cox regression model to estimate rwPFS. Area Under the ROC Curve (AUC) values of the models will be calculated using the Caret and pROC R package and compared using Delong's test.

Patients with missing outcome data will be excluded from the analysis. Covariates whose values will be missing in less than 20% were imputed by using the median or the mode value (for numerical or categorical variables, respectively), while covariates with missing values exceeding 20% will be excluded from the present analysis. 90 All statistical tests will two-tailed, and a p value (P) <0.05 was considered as significant. Statistical analyses will be performed using R software and R Studio (version 4.1.2).

Image omics and model generation methodology

Radiomics Methodology

A team of four radiologists with experience on CT scan/PET images segmentation will identify the Volume Of Interest (VOI) through a semi-automated 3D segmentation process performed with Syngo.via software. An ad hoc designed segmentation protocol will be applied to homogenize the choice of CT/PET sequence on which to perform segmentation and the choice of the lesion to be segmented. Peritumoral area will be obtained through automated augmentation techniques (+5 mm, +10 and +15 mm); if the peritumoral area obtained crosses blood vessels, gas, bone, bile duct, or exceeded the organ edge, the contour will be manually modified to exclude this area. After image pre-processing through different techniques (e.g., gray discretization, intensity normalization, and voxel resampling), radiomic features will be extracted from VOIs and peritumoral areas using the PyRadiomics library in Python. In order to prevent signature overfitting, dimensionality of features is reduced before signature construction, firstly excluding features with high intraclass correlation coefficient and significantly different between the two outcome groups as assessed by one-way analysis of variance (ANOVA). Least absolute shrinkage and selection operator (LASSO) regression and/or Maximum Relevance Minimum Redundancy (MRMR) will be then used for the selection of features that will be included in the final model. The cohort will be split in a training (80%) and testing cohort (20%). Different standard classifiers, such as Random Forest, Multilayer perceptron, Logistic

Regression, Support Vector Machine, CatBoost, AdaBoost, XGBoost, will be trained and evaluated for this task. 91,92

Pathomics Methodology

Pathology slides will be digitalized with Leica Scanscope AT2 and stored as ".svs" files to obtain Whole Slide Images (WSIs). Hematoxilin and Eosin (HE) slides will be digitalized for pathomics purposes. WSIs will be analysed through Slideflow, a Python package that provides a unified Application Programming Interface for building and testing models for histopathology. After color normalization procedures, quantitative pathomics features will be extracted. Model creation and performance evaluation will follow the same methodology discussed in the "Radiomics" workflow. 93

Multimodal integration

We will use several architectures, including logistic regression, classification and regression trees, random forest, multi-layer perceptron, gradient boosted trees (XGBoost), gradient boosting machines (LightGBM) and attentive tabular networks TabNet and we will compare their performance to heuristically decide on the best model choice for follow-up experiments. Our modelling experiments will include different combinations of input embeddings, with concatenation of each data stream permutation to produce fusion embeddings and train models using single-modality or multi-modality of input combinations. All models will be trained multiple times with multiple different data splits to repeat the experiments and compute average metrics and SDs. All defined models will be trained and tested to evaluate the advantage of multimodal predictive systems, as compared to single modality ones for the pre-established classification prediction. To assess model performance, different metrics will be used, including AUC, Sensitivity and Specificity, which will be calculated on the training set through 10-fold cross-validation and on the test set, which will be obtained by randomly splitting the entire cohort in a 80:20 way. The hyperparameter combinations of individual models, such as maximum depth of the trees, number of estimators and learning rate, will be selected within each training loop using a fivefold cross-validated grid search on the training set.^{94,95}

Since these complex models are considered as "black boxes", since they make decisions without clear reasoning, explainability techniques will be adopted to provide insights into how models make predictions, guaranteeing human interpretability. In particular, SHapley Additive exPlanations (SHAP) techniques will be used for both global and local explanations. ⁹⁶

Biological analyses methodology

Genomic analyses

A next generation sequencing (NGS) panel (Oncomine Comprehensive Assay Plus) will be used to perform analysis of various single-gene variants, such as single nucleotide variations (SNVs), indels, fusions, splice Version 1.1, 01Aug2024

Pag. 26 di 32

